21.2.5 Acceptability *Musca sorbens* repellents

Semi-structured interviews will be conducted with all participants over 5 years of age and their primary caregivers on completion of the trial. Interviews will be short (estimated 3 -15 minutes) and, for children, will use age-appropriate questions. The purpose of the interviews is to identify major barriers to adherence to the study protocol and/or to future use of the repellents within or outside of a trial setting. The findings may also point to issues for further exploration in a more naturalistic setting. Indicative interview guides are given in Appendix 8 (Semi-structured interview_Field), and these will be refined and revised during the pilot.

For participants assigned to use the wearable devices, at the start of each data collection visit we will ask whether there have been any difficulties that prevented consistent use and whether any difficulties are foreseen. This will be done in addition to the final interview. Adherence to protocol (continued wearing of the device) will be encouraged according to section 24.

22 Risks, benefits and burden

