12.2 Secondary Objectives

1. To compare the duration of protection offered by different repellent products using the median Complete Protection Time (mCPT)
2. To compare the effectiveness of protection offered by different repellent products using the median effective dose and median effective time
3. To assess the acceptability of the repellent products tested in the field trials using qualitative data from participants.

13 Trial Design

This is a within-subject, non-masked, trial of the use of commercially available insect repellents against *Musca sorbens*, with two consecutive participant groups in the laboratory and in the field, and a primary endpoint of measuring the protective efficacy of each repellent product.

The trial is within-subject to allow comparison of *M. sorbens* contacts on the same participants both before (control) and after (test) application of the repellent or repellent device. This is to mitigate any possible inter-individual attractiveness effects. Control sampling will be conducted before test sampling, to preclude contamination of the control sampling by the test sampling. For this reason, the trial is not masked.

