15.2 Field trial eligibility criteria

1. Participant lives in the designated study site
2. Participating households must be within a one-hour drive of Feya General Hospital
3. Participant considers themselves to be in good health, as does the parent or guardian
4. Participant is aged 3 years and ≤ 12 years
5. Participant has a good understanding of the procedures of the study and agrees to abide to these procedures
6. The parent or guardian of the participant has a good understanding of the procedures of the study and agrees to abide to these procedures
7. Participant is able to communicate well with the investigator or fieldworker who is conducting the study
8. Participant has no known adverse reactions to the commercially available repellents DEET, PMD, IR3535, Picaridin or Permethrin, or to Vanilla
9. Participant has no known history of skin allergies or hypersensitivity to topical creams
10. Participant agrees to a pre-trial skin reactivity test for all the repellents that will be used in the trial
11. If in the event of the participant experiencing an adverse reaction to a repellent during the trial, the participant can request medical advice from the Stronger-SAFE field team nurses if they wish
12. Participant is willing to sit still on a chair outside their house, for sequential periods of up to ten minutes, allowing wild fly contact and landing on the body and face, as much as possible without disturbing fly behaviour
13. Participant agrees not to use any perfumed or scented product, including bathing products, for a 24-hour period before each laboratory session

14. Able and willing to give fully informed assent
15. The parent or guardian has signed informed consent
16. The participant does not become unacceptably upset during the procedures

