17.2 Secondary outcome measures

1. Median Complete Protection Time (mCPT) in laboratory trials only
2. Median Effective Dose (ED₅₀), in laboratory trials only
3. Median Effective Time (ET₅₀), in both laboratory and field trials
4. Acceptability of the repellent interventions among children and their caregivers, in field trials only

18 Participant timeline

A timeline of participant recruitment and enrolment, consent, and completion of the clinical trials is given in Figure 4.

Figure 4. Participant timeline for clinical trials of insect repellents against fly contact by *Musca sorbens*

19 Sample size

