19.2 Field trials sample size

This trial will be powered to detect a protective effect in the intervention (treatment) groups relative to the control groups. To test for 30 % protection (PE) in the intervention arm versus the control arm, assuming a standard deviation of 30% and using 90 % power, 23 children are required in each study group. When allowing for 25 % loss-to-follow-up, the total sample size in each study arm will be 29 people. Equal numbers of male and female participants are preferred.

Not all approximately participants in the wearable repellent device arms of the field trial will be interviewed for intervention acceptability. Based on previous experience, we anticipate that a sample of 15 to 20 child-caregiver pairs, purposively sampled to represent the range of child ages will be sufficient, and further data collection unlikely to yield additional information. However, we will review our data regularly during the data collection process and will adjust the sample accordingly.

20 Enrolment, randomisation and allocation

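### The end-of-trial acceptability interview is limited to participants over five and their own caregivers, which leaves out the youngest families and does not match the interview sample in section 19.2

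*Combined protocol and SAP*

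**What the plan says.** Section 17.2 lists as the fourth secondary outcome "Acceptability of the repellent interventions among children and their caregivers, in field trials only". The matching objective in section 12.2 is "To assess the acceptability of the repellent products tested in the field trials using qualitative data from participants". Neither sets an age limit. The field entry criterion in section 15.2 reads "Participant is aged 3 years and ≤ 12 years".

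Section 21.2.5 sets the rule for the final interview: "Semi-structured interviews will be conducted with all participants over 5 years of age and their primary caregivers on completion of the trial". It applies to participants generally and is not confined to one type of product.

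Section 19.2 describes the interview sample differently. It says that not all "participants in the wearable repellent device arms of the field trial will be interviewed for intervention acceptability", and anticipates that "a sample of 15 to 20 child-caregiver pairs, purposively sampled to represent the range of child ages will be sufficient".

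For wearable-device users only, section 21.2.5 adds a second source: "at the start of each data collection visit we will ask whether there have been any difficulties that prevented consistent use". This comes on top of the final interview. Section 24.2 repeats the visit question without an age limit.

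**The concern.** An age floor for interviewing a small child is easy to understand. The difficulty is that the wording attaches the caregiver to the child, so a caregiver whose child is too young to interview drops out as well. The plan gives no reason for that, and these caregivers are able informants.

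They are also relevant ones. Under section 21.2.4 the caregiver may put the device on the child. Under section 24.1 the caregiver receives the reminder messages and the visit on the day before testing. Under section 22.2.7 caregivers are told how important it is to keep topical product from reaching the eye. The stated purpose of the interviews is to find barriers to adherence and to later use, and section 16.2.2 says that field outcome measures will inform whether repellents enter the Phase 3 trial. Acceptability learned only from families of older children would then be carried over to an age range that includes families who had no final interview.

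**Working it through.** **The plan's own figure.** The documents give no share of children aged five or under. The only stated figure needed is the arm size, which turns a share into a count. Section 19.2 uses a difference of 30%, an SD of 30% and 90% power. Alpha is not stated; 0.05 two-sided is assumed here.

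- Normal approximation: n = 2 × (1.960 + 1.282)² × (30/30)² = 21.0, rounded up to 22. The two-sample t version gives 22.02, rounded up to 23, which is the plan's number.
- Allowance for 25% loss: 23 × 1.25 = 28.75, rounded up to 29, as stated. (Dividing by 0.75 would give 31. The stated 29 is used below.)
- Section 13.2 allows at most four product arms plus a control arm, so product arms hold at most 4 × 29 = 116 children.

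**Share without a final interview if section 21.2.5 governs.** Assumption: ages are spread evenly over the entry range. Share = excluded age width / total age width.

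| Reading | Share | Of 29 per arm | Of 116 in product arms |
|---|---|---|---|
| Completed years 3-12, ages 3-4 excluded | 2/10 = 20% | 5.8 | 23.2 |
| Exact age 3.0-12.0, up to 5.0 excluded | 2/9 = 22% | 6.4 | 25.8 |
| Completed years 3-12, ages 3-5 excluded | 3/10 = 30% | 8.7 | 34.8 |
| Exact age 3.0-12.0, under 6.0 excluded | 3/9 = 33% | 9.7 | 38.7 |
| Entry read as older than three (years 4-12), age 4 excluded | 1/9 = 11% | 3.2 | 12.9 |
| Entry read as older than three (years 4-12), ages 4-5 excluded | 2/9 = 22% | 6.4 | 25.8 |

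The last two rows fit less well with section 22.4.2, which expects participants as young as three.

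**If section 19.2 governs instead.** In a sample of 15 to 20 pairs spread in proportion to age, the youngest group at 20-33% would be 15 × 0.20 = 3 to 20 × 0.333 = 6.7, so about 3 to 7 pairs.

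**The two sections side by side.**

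- Number: 21.2.5 says all participants over five; 19.2 says 15 to 20 pairs. These conflict.
- Arms: 21.2.5 does not restrict the final interview by product; 19.2 speaks of the wearable arms.
- Age: 21.2.5 stops at over five; 19.2 wants the children's ages represented. If that means 3 to 12, the sections conflict on age. If it means only ages above five, they agree and the gap stands.

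**Other sources for the youngest.** The visit question (21.2.5, 24.2) and the possible unannounced visits (24.1) reach wearable users only and concern problems with use. The pilot interviews (21.2.2) follow diluent alone and serve to refine the topic guides. None of these gives a topical-arm family with a child of five or under an account of product acceptability.

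**The case against.** The strongest case against has four parts.

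1. A reader might infer that nobody reports for the youngest children, or that no acceptability record for them can exist. The documents do not support that. Wearable users of any age are asked about difficulties at each visit, and the pairs in section 19.2 may include families of young children. This part stands, and it confines the gap to the final interview. It does not close the gap: the visit question supplements the interview, and it does not reach the topical arms.
2. A reader might infer that acceptability will look better than it is, because older children face fewer barriers. Nothing in the documents says so. Section 22.4.2 concerns the difficulty of sitting still for observation at a young age, not the product. The direction of any effect is unknown.
3. Counting the gap over all five groups (145 children) would be wrong, because the control group receives no product. The base is at most 116, and fewer if fewer than four products are tested. A headcount share also says little about a small purposive sample.
4. The outcome is qualitative and secondary, and the interview guides are to be revised during the pilot. This bears on severity. It does not explain why caregivers of the youngest are ineligible, since revising the guides does not by itself change who is interviewed.

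**Conclusion.** The point holds as a minor one. On the plain reading of section 21.2.5, children of five or under and their caregivers have no final acceptability interview, although the outcome has no age limit and entry starts at three. The gap is clearest in the topical arms, where no comparable source exists. Sections 21.2.5 and 19.2 conflict on how many are interviewed and probably, though not certainly, on ages.

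The size depends on an age mix that the documents do not give. Under an even spread it is about 20-33% of children, or 11-22% if entry is read as older than three. All of these figures assume that 21.2.5 governs. The primary endpoint, its analysis and the sample size are untouched.

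**What to change.** In section 21.2.5, apply the age limit to the child's interview only, and make the primary caregivers of children aged five or under eligible for the caregiver interview in both topical and wearable arms. State whether a child who is exactly five counts as over five. Reconcile sections 21.2.5 and 19.2 on who is interviewed, in which arms and how many. Describe the findings by child age where numbers allow; with only a few youngest families this would be a description, not a comparison.

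The cost is a few more interviews of 3 to 15 minutes by the same team, or none if the total is held fixed and spread over the ages. The change needs to be made before the end-of-trial interviews.

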22.1 Risk from eye-seeking flies, *Musca sorbens*

22.1.1 Laboratory trials

Participants will be exposed to laboratory-reared populations of *Musca sorbens*. These flies have been reared in captivity for over six generations and carry no risk of Ct transmission. Participants will only be exposed to fly contact on their arms, and after completion of testing, will immediately be instructed to wash their arm. Therefore, the modified arm-in-cage assay presents only negligible risk.

22.1.2 Field trials

Participants will be exposed to natural populations of eye-seeking flies, primarily *Musca sorbens*. Because we will study the protective efficacy of these insect repellents outside the participant's houses, they will not be exposed to any greater risk than that which they experience day-to-day. However, participants will be asked to remain seated and not brush away flies from their eyes during observation periods. Previous observations in the study setting indicate that not brushing away flies is normal behaviour. Further, field work will be conducted in part by the Stronger-SAFE team ophthalmic nurses. During recruitment, children will be screened for trachoma and their trachoma status recorded. After participation in the trial is complete, all children with trachoma will be treated with Azithromycin.

22.2 Risk from insect repellent products

Up to six active ingredients (repellent products and a repellent synergist) may be used in this study, the selection of which will be made following laboratory studies that will be conducted in an insect testing facility at LSHTM, London, using laboratory-reared *Musca sorbens*. These are:

- DEET (N,N-Diethyl-meta-toluamide)
- IR3535 (3-[N-butyl-N-acetyl]-aminopropionic acid ethyl ester)
- Picaridin (2-(2-hydroxyethyl)-1-piperidinecarboxylic acid 1-methylpropyl ester)
- PMD (para-Menthane-3,8-diol)
- Permethrin ((m-Phenoxybenzyl)-cis,trans-3-(2,2-dichlorovinyl)-2,2-dimethylcyclopropanecarboxylate)
- Vanillin (4-Hydroxy-3-methoxybenzaldehyde)

A full assessment of the risk associated with the use of the above repellents is given in sections 22.2.1 to 22.2.6 below. Here, particular attention is given to adverse incidents and events associated with repellents in the eye or on the face. Safety information regarding the repellent active ingredients used in the trial have been assessed, material safety data sheets (MSDS) and labels have been read to be sure they are safe for human use. Participants will be given an information sheet explaining the details of the ingredients and what to do if they have a reaction to the product after completion of the test. Repellent products will not be applied to broken skin.

General risks to participants associated with involvement in this study will be addressed by adhering to ICH GCP (58), the Declaration of Helsinki (59), the Data Protection Act (60) and all applicable regulatory requirements. There will be no benefit to participants. The results of this study will be used to design the trachoma transmission-blocking intervention that will be rolled out in Stronger-SAFE Phase 3, a cluster-randomised controlled trial.

22.2.1 DEET

N,N-Diethyl-meta-toluamide (DEET) is a colourless liquid that is the most common active ingredient in insect repellents. It may cause eye and skin irritation and may be harmful if swallowed.

Specifically with regards to the use of DEET on children, this repellent should not be applied to children under two years of age, further, this product should not be applied to the hands of

children under 12 years of age (61). This is to reduce the risk of ingestion by hand to mouth behaviour. It is recommended that DEET should not be applied near the eyes and mouth, children should not be allowed to handle the product and when applying on children, it should first be applied to other hands and then put on the child (62).

DEET has been found to cause serious eye effects in rabbits, where eye irritation and corneal opacity were observed but both cleared by day three and seven respectively (62). The same document noted that LD50 values in this study were “quite high”, with four grams of test material being applied per kilogram of body weight. With reference to this trial, 18.85 mg of active ingredient would be applied to the cheeks at the highest dose, 20 %, which is 0.47 % of four grams. For a child of body weight 10 Kg this would equate to 4.59 % of the AEL (Appendix 9). The same guidelines stated “If used on the face, spray on hands first and then apply sparingly and avoid eyes. Do not spray directly onto face.”, indicating acceptability of use on the face. In 2010, the European commission conducted a risk assessment to human health for DEET. They found that an R statement of R36 (irritating to eyes) was not warranted, however, because of the scores for corneal opacity in rabbits, they gave a GHS (Globally Harmonized System of Classification and Labelling of Chemicals) Category 2 (Figure 9), with an H statement of H319 (Causes serious eye irritation).

OPP Criteria, Signal Words, Symbol, and Hazard Statements	GHS Criteria, Signal Word, Pictograms, and Label Statements

PRIMARY EYE IRRITATION
 
Category I Corrosive (irreversible destruction of ocular tissue) or corneal involvement or irritation persisting for more than 21 days.
 
DANGER No symbol Corrosive. Causes irreversible eye damage.
 
Category II Corneal involvement or irritation clearing in 8-21 days.
 
WARNING No symbol Causes substantial but temporary eye injury.
 
Category III Corneal involvement or irritation clearing in 7 days or less.
 
CAUTION No symbol Causes moderate eye irritation.
 
Category IV Minimal effects clearing in less than 24 hours.
 
No signal word, symbol or hazard statement required. Registrant may choose to use Category III statement.
	
SERIOUS EYE DAMAGE/EYE IRRITATION
 
Category 1 Effects on the cornea, iris or conjunctiva that are not expected to reverse or that have not fully reversed within 21 days.
 
DANGER Corrosion symbol in diamond. Causes severe eye damage.
 
Category 2A Effects on the cornea, iris or conjunctiva that fully reverse within 21 days.
 
WARNING Exclamation mark in diamond. Causes severe eye irritation.
 
Category 2B Effects on the cornea, iris or conjunctiva that fully reverse within 7 days.
 
WARNING No symbol Causes eye irritation.

Figure 9. A comparison of chemical hazard classification and labeling: Office of Pesticide Programs (OPP) and the Globally Harmonized System of Classification and Labelling of Chemicals (GHS) (63). DEET was found to be in GHS category 2 (level unspecified) (61).

DEET has caused adverse reproductive and fetal effects in animals, and may cause central nervous system effects. There are no known carcinogenic chemicals in this product. The safety of daily application of (DEET) in the second and third trimesters of pregnancy was assessed as part of a double-blind, randomized, therapeutic trial of insect repellents for the prevention of malaria in pregnancy. The results of the study suggest that the risk of DEET accumulating in the fetus is low and that DEET is safe to use in later pregnancy (64).

By having the ophthalmic nurse apply the DEET directly to the children's face, we will avoid DEET application to the children's hands. It is possible that the child may, over the course of the day's testing, touch their face and then their mouth. However, DEET is commercially available for use on children above the age of two, despite the recommendation that it is not applied to their hands. From this, we can assume that the risk presented from skin (e.g. elsewhere on the child), to hand, to mouth is negligible, presumably because the amount of DEET that is transferred in this way is very small. Further to that, the amount that will be applied in this trial (a circle of 6 cm diameter)

will overall be much smaller than that which would be applied to the child's whole body, for example to repel mosquitoes, which it is frequently used for. Finally, for topical repellent testing, the ophthalmic nurse and team will be present at the house and near the participant all day, and will try to dissuade the child from this type of behaviour.

Current European Union guidelines concerning the risk to consumers for the use of DEET sets the AEL_{repeated} (acceptable exposure level for repeated use) at 8.2 mg/kg body weight (bw)/day (61). For an estimation of the percentage of this AEL that will be topically applied of active ingredient, for a hypothetical dose range of maximum 20 % and a range of hypothetical children's body weights, see Appendix 9, for the material safety data sheet (MSDS) see Appendix 10.

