16.2.2 Field trials application rate

Topical repellent will be applied to a circular area on the cheek. An average diameter of 6 cm would give a surface area of 28.3 cm². As such, 0.05 ml (50 µL) of product will be applied to each cheek at the appropriate concentration, never exceeding 20 %. Topical repellents will be applied at least 3 cm (three finger-breadths) below the eye and positioned away from the nose and mouth.

Due to the differences in surface area under observation in the laboratory and field trials, with greater skin surface areas in the former (application on the arm) leading to greater amounts of active ingredient being applied, there is a risk that efficacy in the laboratory will be greater than that experienced in the field. However, it should be emphasised that the aim of the laboratory trials is to inform which repellents can be taken into the field trial for testing, as this is the context in which such a product would be used. Therefore, while both studies are merited, the Protective Efficacy and other outcome measures as calculated in the field trial will be those that are used to inform inclusion of repellents as a fly-control intervention in the Stronger-SAFE Phase 3 RCT.

17 Study outcomes

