21.2.3 Topical repellents

Eligible **participants** will be randomly allocated in equal proportions to the study groups, as per section 13. The repellent products and product formulations to be tested will be determined before the study commences. Each study participant will test only one product type, to minimise participant discomfort. Participants will be advised not to apply any cosmetics associated with a strong scent, such as perfume, hand cream, body wash, or other scented products. Additionally, volunteers will be asked not to consume spicy foods, i.e. curries, chillies and garlic for the 12 hours prior to the tests. This will be verified with the participants prior to the commencement of any tests.

The participants face will first be washed with unscented soap then rinsed with water and towel dried. The participant will then be seated comfortably on a chair outside their house, facing the investigators (entomological field worker and nurse), and will be instructed to refrain from touching the face or brushing away landing flies. For the first test, the diluent alone (50 µL) will be tested as a control. This will be applied to the participant's face (cheeks) and allowed to dry for one minute. The participant's face will then be videoed for ten minutes by the investigator or field laboratory assistant. During this time period, fly behaviour will be manually recorded and scored. The video footage will retrospectively be analysed for (i) fly-eye (ii) fly-nose (iii) fly-mouth and (iv) fly-face contact. After this ten-minute period of control measurements, the pre-allocated topical repellent will be applied to a circular area on the participant's cheek by the Stronger-SAFE field

team nurses. Topical repellents will be applied in a 6 cm diameter circle on the cheek, at least 3 cm below the eye and positioned away from the nose and mouth. The repellent will be allowed to dry for one minute, then the videoing and observation will be repeated for another ten-minute period. Test measurements will then be repeated hourly for five further time points (Figure 7). After the final time point, the participant will be provided with soap and water to clean off the topical repellent.

[figure not shown]

Figure 7. Study design for estimation of personal protection by topical repellents from fly-eye and fly-face contacts by *Musca sorbens*. This process will be repeated for each of 29 participants.

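### The stated 4.59 % of the DEET acceptable exposure level for a 10 kg child does not follow from the protocol's own figures, which give 23.0 % of the level as applied

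*Combined protocol and SAP*

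**What the plan says.** All references are to the combined protocol and SAP.

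- **Amount applied.** Section 22.2.1 (DEET) states: "18.85 mg of active ingredient would be applied to the cheeks at the highest dose, 20 %, which is 0.47 % of four grams".
- **Share of the limit.** The next sentence reads: "For a child of body weight 10 Kg this would equate to 4.59 % of the AEL (Appendix 9").
- **The limit.** Later in section 22.2.1 the European Union AEL is given, described as the "acceptable exposure level for repeated use) at 8.2 mg/kg body weight (bw)/day".
- **Basis of the percentage.** The same paragraph refers the reader to Appendix 9 with the words "For an estimation of the percentage of this AEL that will be topically applied of active ingredient", for concentrations up to 20 % and a range of hypothetical body weights. The DEET section states no absorption or other reducing factor.
- **How the amount arises.** Section 16.2 sets 1 ml per 600 cm². Section 16.2.2 gives a 6 cm circle (28.3 cm²) and 50 µL "of product will be applied to each cheek at the appropriate concentration, never exceeding 20" %. Section 21.2.3 uses the singular for the site: "Topical repellents will be applied in a 6 cm diameter circle on the cheek, at least 3 cm below the eye".

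**The concern.** The amount, the body weight and the limit all stand in section 22.2.1, so the percentage should follow from them by one division. It does not.

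The figure matters because of where it sits. It is the only exposure figure adjusted for body weight that the main text gives for a topical repellent on children's faces. The IR3535 and picaridin sections (22.2.2 and 22.2.3) state a limit but leave the percentage to Appendix 9. The comparison just before it, 0.47 % of four grams, cannot take its place: it sets a total amount against an animal dose described as "with four grams of test material being applied per kilogram of body weight", so it is not weight-adjusted.

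A reader, including an ethics committee, would take the margin to this daily limit to be about 22-fold. The stated inputs give about 4.3-fold.

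**Working it through.** **Inputs**

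- Application rate: 1 ml per 600 cm² (section 16.2)
- Circle diameter: 6 cm, radius 3 cm (section 16.2.2)
- Maximum concentration: 20 % (section 16.2.2), taken as 200 mg/ml; this reproduces the plan's own amount
- Body weight: 10 kg (section 22.2.1)
- DEET AEL: 8.2 mg/kg/day (section 22.2.1)

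**Step 1. Reproduce the plan's amount.**
- Area per cheek: π × 3² = 28.27 cm²
- Volume per cheek: 28.27/600 = 0.0471 ml
- Two cheeks at 200 mg/ml: 2 × 0.0471 × 200 = 18.85 mg

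This agrees with section 22.2.1. So does 18.85/4000 = 0.47 %.

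**Step 2. Share of the AEL.**
- Limit at 10 kg: 8.2 × 10 = 82 mg/day
- Share: 18.85/82 = 22.99 %, against 4.59 % stated
- Ratio: 22.99/4.59 = 5.0
- Margins: 82/18.85 = 4.35-fold, against 1/0.0459 = 21.8-fold

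**Step 3. Other readings of the applied amount (20 %, 10 kg).**

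| Reading | Amount | Share of 82 mg |
|---|---|---|
| Two cheeks, exact area | 18.85 mg | 23.0 % |
| Two cheeks, 50 µL each | 20 mg | 24.4 % |
| One cheek, exact area | 9.42 mg | 11.5 % |
| One cheek, 50 µL | 10 mg | 12.2 % |

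None gives 4.59 %.

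**Step 4. Solve back from 4.59 %, changing one input at a time.**
- Amount: 0.0459 × 82 = 3.76 mg
- Body weight: 18.85/(0.0459 × 8.2) = 50.1 kg
- Extra multiplier: 3.76/18.85 = 0.20

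Several slips would fit: the 20 % applied a second time, a 20 % absorption factor, a 50 kg row, or a 4 % concentration row (18.85 × 4/20 = 3.77 mg, 4.60 %). With 18.85 mg, the factor of 0.20 and the 50 kg row both give 4.598 %, which rounds to 4.60 %. If the amount was first rounded to 18.8 mg, the factor gives 3.76/82 and the 50 kg row gives 18.8/410, both 4.585 %, which rounds to the printed 4.59 %. The arithmetic therefore cannot tell these causes apart.

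**Step 5. Other body weights at 18.85 mg** (illustrative; the protocol gives no expected weights): 15 kg 15.3 %, 20 kg 11.5 %, 30 kg 7.7 %, 50 kg 4.6 %.

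**Step 6. Possible carry-over.** Assuming the same 18.85 mg and 10 kg, the IR3535 limit of 6 mg/kg/day (section 22.2.2) gives 18.85/60 = 31.4 %. The picaridin limit of 3.1 mg/kg/day (section 22.2.3) gives 18.85/31 = 60.8 %. If Appendix 9 carried a factor of 0.20 throughout, it would show about 6.3 % and 12.2 %. Whether it does is not known.

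**The case against.** **The method may be in Appendix 9.** The disputed sentence cites that appendix, which was not available for this review. It may state an absorption factor, and the protocol does not say whether the AEL refers to applied or absorbed amounts. The wording about topical application is loose and recurs almost unchanged for the other two products. This stands as a limit on what can be said about the cause. It does not rescue the sentence. The 4.59 % is presented as the equivalent of the 18.85 mg applied, and the section calls it a share applied to the skin. An absorbed-dose figure would contradict that description. Where the protocol does rely on a transfer rate, for permethrin in section 22.2.5, it states it (0.49 % per day).

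**A lower-concentration row may have been copied.** A 4 % row gives 4.60 %. That could explain the slip, but the sentence is tied to the highest dose, 20 %, so the figure would still be wrong there.

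**The consequence is small.** Much of this stands. Every DEET value above is below 100 %. The limit is for repeated use, whereas section 21.2.3 describes one application, washed off after the last time point. The 10 kg child is hypothetical and heavier children have lower percentages. The AEL does not measure eye irritation, to which section 22.2 gives particular attention. No endpoint, eligibility rule or concentration cap depends on the percentage.

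**The four-gram comparison works the other way.** This is right as to direction: adjusted for 10 kg it becomes 18.85/40000 = 0.047 %, more favourable than printed. It is mentioned only because, as written, it is not a weight-adjusted substitute for the AEL figure.

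**Conclusion.** The concern holds. On the figures in section 22.2.1, a 10 kg child receives 23.0 % of the AEL as applied, not 4.59 %. The exposure share is understated, and the apparent margin overstated, by a factor of 5.0. Across the applied amounts that the text allows at 20 %, the share runs from 11.5 % to 24.4 %.

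This rests on the stated amount, weight and limit, and on the section's description of the percentage as applied. Confidence is high that the printed figure does not follow from the text. Whether the true margin is overstated five-fold depends on Appendix 9, and no cause is asserted. No exceedance is shown. The sentence should be corrected because it is a safety figure that readers will rely on.

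**What to change.** Reconcile both statements in section 22.2.1 with Appendix 9, and put the formula and inputs beside the figure. Then, according to what Appendix 9 shows:

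1. If no further factor was intended, or a row for another concentration was copied, restate the figure as 18.85/(8.2 × 10) = 23.0 % of the AEL, as applied.
2. If an absorption factor was used, state it with its source, label the percentage as absorbed, and amend the wording that calls it applied.
3. If the body weight is the slip (50 kg gives 4.60 %), correct the weight and also give the 10 kg value.

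In the same pass, confirm whether one cheek or two is meant, since sections 16.2.2 and 21.2.3 differ in wording and the percentage halves with one. Check the IR3535 and picaridin entries of Appendix 9 for the same factor. Correct any other document only where it repeats the figure.

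The cost is one corrected sentence and one checked table. Under the first option the stated margin becomes less favourable. This is a request to reconcile the figures; no change of dose is proposed.
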